- Group 2 – Screened positive for SUD on the ASSIST but not enrolled in the study due to screening out, not completing baseline, or not consenting. A report of the patient's ASSIST results was provided to the patient's PCP through the EMR. The patient's PCP's nurse contacted the patient to deliver a brief intervention and referred them to behavioral health or specialty treatment if indicated.
- Group 3 – Screened positive for SUD on the ASSIST and assigned to the Comparison Condition. As in Group 2, a report of the patient's ASSIST results was provided to their PCP in the EMR. The PCP's nurse contacted the patient to deliver a brief intervention and referral to behavioral health or specialty treatment if indicated. These patients received an initial email notification—with up to 9 email and text reminders, 5 calls, a mailed flyer, and calls to collateral contacts—to complete additional study assessments.
- Group 4 – Screened positive for SUD on the ASSIST and assigned to the *Connect2BWell* Condition. The patient was transitioned seamlessly from the online *Connect2BWell* screening questions and consent form to the intervention portion of the session. After the session, a report of the patient's ASSIST results was assigned to the study's Nurse Care Manager (NCM) in the EMR. The study's NCM contacted the patient to deliver a brief intervention guided by the *Connect2BWell* Clinical Dashboard and made a referral to behavioral health or specialty treatment if indicated. The patient received additional *Connect2BWell* online sessions at 1 and 3 months follow-up. Each online session was followed by a Clinical Dashboard-guided one-on-one session with the study's NCM. The patient also received 6 months' of stage-matched text messages and access to a patient portal with tools and activities to support and facilitate change. These patients received an initial email notification and the same schedule of reminders as the Comparison group to complete additional study assessments.
- Group 5 – Recruited via the Targeted Approach and assigned to the Comparison Condition. These patients had already completed CHC's standard SBIRT screening and brief intervention.

- Group 6 – Recruited via the Targeted Approach and assigned to the *Connect2BWell* Condition. While these patients had already completed CHC's standard SBIRT screening and brief intervention, their ASSIST results were assigned to the study NCM in the EMR and they received the study intervention.

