- Groups 3 and 5 comprise the Comparison group and groups 4 and 6 comprise the *Connect2BWell* treatment group. Both groups are prompted to complete follow-up online assessments 3, 6, and 9 months. Non-respondents received up to 9 email and text reminders, 5 calls, a mailed flyer, and calls to collateral contacts.

Analysis Plan

The analysis will use mixed effects models that account for repeated measures within participants through a random intercept for participants. Fixed effects will include group (treatment vs control), time, and time-by-group interaction. Analyses will be conducted for the primary outcome measure of change from baseline in days of use of the most problematic drug in the previous 30 days at 9 Months. Secondary outcome measures include the change from baseline in ASSIST score for most problematic drug at 9 months and the change from baseline in ASSIST score for total substance involvement at 9 months as well as the change from baseline in depression at 9 months.

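### The primary model names no baseline covariate; if patients were randomised about 1:1, or baseline slopes are similar, adjusting for baseline is no less precise in large samples and usually more

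*Combined protocol and SAP*

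**What the plan says.** The Analysis Plan is a single paragraph. The models "account for repeated measures within participants through a random intercept for participants", and "Fixed effects will include group (treatment vs control), time, and time-by-group interaction". The primary outcome is "change from baseline in days of use of the most problematic drug in the previous 30 days at 9 Months". Three secondary outcomes follow the same pattern: the sentence begins "Secondary outcome measures include the change from baseline in ASSIST score for most problematic drug at 9 months" and goes on to the total-involvement ASSIST score and depression. No baseline value is listed as a covariate, and nothing says that the two arms share a baseline mean.

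Three other statements matter here:

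- Group 2 contains patients "not enrolled in the study due to screening out, not completing baseline, or not consenting". Baseline should therefore exist for enrolled patients.
- On follow-up, "Both groups are prompted to complete follow-up online assessments 3, 6, and 9 months", and "Non-respondents received up to 9 email and text reminders, 5 calls, a mailed flyer, and calls to collateral contacts". Some non-response was expected.
- Group 3 is described as "Screened positive for SUD on the ASSIST and assigned to the Comparison Condition". The document does not say that assignment was random, and it gives no allocation ratio.

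**The concern.** The plan does not say whether the response is the change score at 3, 6 and 9 months or raw days of use with baseline as the first time point. It also does not say whether time is categorical. With categorical time and complete data this makes no difference to the estimate: both readings give the unadjusted difference in mean change at 9 months. In the raw-days version baseline is in the model as a response, but the free group effect at baseline means it does not adjust the contrast.

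A change score subtracts the whole of the baseline value. That is the best use of baseline only when 9-month use rises one day for each extra baseline day. With any other slope, subtraction removes too much or too little, and the leftover baseline variation inflates the standard error. A chance imbalance at baseline is also carried into the estimate. What is at stake is the width of the confidence interval and the power of the primary comparison, and likewise for the three secondary outcomes.

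**Working it through.** **Inputs.** The outcome, model terms and visit times come from the Analysis Plan and the follow-up text just before it. The document gives no correlation, SD, sample size, allocation ratio, retention or power, so there is no planned figure to reproduce. Everything below is an assumed range, for randomised 1:1 allocation unless stated.

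**1. Complete data, common slope.** Let the baseline SD be 1, k = SD at 9 months / SD at baseline, and ρ the baseline-to-9-month correlation. The slope is ρk. Per patient:

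- planned variance ∝ 1 + k² − 2ρk
- adjusted variance ∝ k²(1 − ρ²)
- difference = (1 − ρk)², which is never negative and is zero only when the slope is 1.

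| k | ρ = 0.2: planned → adjusted (cut) | ρ = 0.5 | ρ = 0.8 |
|---|---|---|---|
| 1 | 1.60 → 0.96 (40%) | 1.00 → 0.75 (25%) | 0.40 → 0.36 (10%) |
| 0.8 | 1.32 → 0.61 (53%) | 0.84 → 0.48 (43%) | 0.36 → 0.23 (36%) |
| 1.25 | 2.06 → 1.50 (27%) | 1.31 → 1.17 (11%) | 0.56 → 0.56 (0%) |

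At k = 1 and ρ = 0.5, the unadjusted contrast needs 1/0.75 = 1.33 times as many patients for the same precision. A simulation of a bounded 0–30 day outcome (ρ about 0.6) gave adjusted/planned variance ratios of 0.78 to 0.82, with essentially the same mean effect.

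**2. Missing follow-up.** Suppose a fraction R of patients keep follow-up, the rest lose all of it completely at random, SDs are equal and the covariance is compound symmetric.

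- Change-score response: planned/adjusted = 2/(1 + ρ), so the cuts stay at 40% / 25% / 10%.
- Raw-days response, where baseline-only patients stay in the planned model: planned/adjusted = 1 + R(1 − ρ)/(1 + ρ).

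| R | ρ = 0.2 | ρ = 0.5 | ρ = 0.8 |
|---|---|---|---|
| 0.7 | 1.47 (cut 32%) | 1.23 (19%) | 1.08 (7%) |
| 0.5 | 1.33 (25%) | 1.17 (14%) | 1.06 (5%) |

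Simulation at R = 0.7 (3,000 trials, n = 400, visits at 0, 3, 6 and 9 months) gave 1.47 / 1.25 / 1.08 for raw days and 1.66 / 1.36 / 1.11 for change scores. With 11% dropping out before each visit (0.89³ ≈ 0.70 left at 9 months) the ratios were 1.50 / 1.23 / 1.10 and 1.61 / 1.29 / 1.11.

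**3. Unequal allocation and different slopes.** Let the arm shares be p₁ and p₀, slopes b₁ and b₀, residual variance s = 0.5, and B = p₁b₁ + p₀b₀. Then n × variance is:

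- planned: Σ[s + (1 − b)²]/p
- common-slope adjusted: Σ[s + (b − B)²]/p
- with centred baseline-by-group: s/p₁ + s/p₀ + (b₁ − b₀)²

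For 3:1 with slopes 0.2 (larger arm) and 1.0, B = 0.4:

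- planned: 1.14/0.75 + 0.50/0.25 = 3.52
- common slope: 0.54/0.75 + 0.86/0.25 = 4.16
- with interaction: 0.67 + 2.00 + 0.64 = 3.31

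So common-slope adjustment loses precision here, and the interaction restores the gain. Simulation (6,000 trials, n = 800) gave 3.43 / 4.18 / 3.25. Ignoring the estimated centring mean would report 0.67 + 2.00 = 2.67 in place of 3.31.

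For 3:1 with slopes 0.4 and 0.8 the three values are 3.31 / 3.04 / 2.83. For 1:1 with slopes 0.2 and 1.0 they are 3.28 / 2.64 / 2.64, so at 1:1 the interaction adds nothing.

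**4. Effect on the estimate.** With complete data and a common slope, planned minus adjusted = (slope − 1) × the observed baseline difference. At k = 1 that is −0.8 / −0.5 / −0.2 day per day of baseline imbalance for ρ = 0.2 / 0.5 / 0.8.

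**The case against.** The strongest reply is that nothing here is an error. Under randomisation the change contrast is valid, and the document lacks every quantity needed to size the loss: the gain in the settings above runs from 53% to none, and common-slope adjustment can even lose. That stands as a limit on size and severity. It does not make the listed contrast the better choice, because under the stated conditions it cannot beat the adjusted one in large samples.

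A second reply is that a random intercept with a time-by-group term most naturally means raw days including baseline. The matching step would then be a common baseline mean, and a covariate model drops patients with baseline only. The reading is fair, and the gain against the planned model is smaller under it. But at 1:1, in the settings examined, the covariate model is as precise as the common-baseline-mean model even after dropping those patients, because they inform only the shared baseline mean, which cancels from the contrast.

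Third, the plan is one paragraph, so a baseline term may be intended. That is possible, but as written it is absent.

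Finally, conduct is described in the past tense. If outcomes by arm had already been seen, replacing the primary model would carry a credibility cost. This bears on how to report the adjusted result, not on whether the gap exists.

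**Conclusion.** The concern holds as an efficiency point that should be acted on. As listed, the model gives an unadjusted change contrast for the primary outcome and for all three secondary outcomes.

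If assignment was randomised, the planned analysis is valid but in general wastes precision. The large-sample guarantee needs 1:1 allocation among analysed patients or similar baseline slopes in the two arms. With unequal allocation and very different slopes it needs a baseline-by-group term.

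The size cannot be fixed from the documents. A variance reduction of 10% to 40% (equal SDs, complete data, ρ from 0.8 down to 0.2) is a reasonable working range. It shrinks if raw days was the intended response and follow-up is incomplete, and it vanishes if the slope is 1.

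If assignment was not randomised, the planned and adjusted contrasts can estimate different things and neither is guaranteed unbiased. The precision argument then does not settle the choice.

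**What to change.** State in the Analysis Plan whether baseline is a response or a covariate, that time is categorical, whether assignment was randomised, and the allocation ratio. Then:

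- Model days of use at 3, 6 and 9 months with group, time and group-by-time, add baseline days of use and baseline-by-time, and report the 9-month group contrast.
- If allocation was unequal, add a centred baseline-by-group term that may vary by time, with a standard error that allows for the estimated centring mean.
- Do the same for both ASSIST scores and depression, each with its own baseline.
- If raw days including baseline was intended and assignment was randomised, a model with a common baseline mean and a less restrictive covariance than the single random intercept is an alternative that keeps baseline-only patients.
- If assignment was not randomised, or if outcomes by arm had already been seen, report the adjusted result beside the planned one. Without randomisation, do not present it as a pure precision gain.

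The cost is a few sentences, with no new data or patients. Patients with no follow-up leave the covariate model. That is no loss against a change-score analysis, but under the raw-days reading it drops patients whom the planned model keeps. In the completely-at-random settings above, the adjusted contrast was still the more precise.
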